2.3. Benefit/Risk Assessment

[REDACTED]

[REDACTED]

The protocol has been designed to minimize the risk to patients. Patients will be monitored to detect AEs during the study and will be followed appropriately to ensure resolution of AEs. Standard hematology, chemistry, urinalysis, lipid levels, and ECGs will be obtained and monitored for abnormalities. Prior to administration of a dose up to 20 mg TERN-201, available PK from the 10 mg cohort will be assessed to predict that projected exposures are below the limits noted above.

Taking into account the measures taken to minimize risk to patients in this study, the potential risks identified in association with TERN-201 are justified by the anticipated benefits that may be afforded to patients with NASH.

Please refer to the Investigator's Brochure for a summary of data on TERN-201 and guidance for Investigators.

3. Objectives and Endpoints

Primary Objective:

- To characterize the safety and tolerability of TERN-201 versus placebo for 12 weeks in non-cirrhotic presumed NASH patients, with a clinical or histological NASH diagnosis

Secondary Objectives:

- To assess the plasma and urine PK of TERN-201 for 12 weeks in non-cirrhotic presumed NASH patients
- To assess the PD effect of TERN-201 versus placebo for 12 weeks on plasma VAP-1/SSAO activity in non-cirrhotic presumed NASH patients

Exploratory Objectives:

- To assess the plasma and urine PK of TERN-201 metabolites (including TRN-001021 and TRN-001744) at steady state
- To assess the effect of TERN-201 versus placebo on imaging assessments and blood biomarkers of NASH activity
- To assess the effect of TERN-201 versus placebo on biomarkers of inflammation
- To explore the potential for TERN-201 to improve proteinuria due to endothelial effects
- To explore other PD markers, and overall exposure-response and dose-response relationship of TERN-201, as applicable
- To explore the exposure-response and dose-response relationship, as applicable, of TERN-201 and baseline patient characteristics such as soluble VAP-1 (sVAP-1), body mass index (BMI), diabetes mellitus, and others

Endpoints:

Primary Endpoint:

- Overall safety assessed by treatment emergent AEs (TEAEs), and treatment emergent clinical safety laboratory abnormalities

Secondary Endpoints:

- Plasma and urine PK parameters for TERN-201

- Percent change from baseline in plasma VAP-1/SSAO activity

Exploratory Endpoints:

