Appendix 1: Clinical Laboratory Tests

The tests detailed in [Table 2](#) will be performed by the central laboratory. Local laboratory testing should only be used in the event that central laboratory results would not available in time for necessary clinical decision making. If a local sample is required, it is important that a sample for central analysis is obtained at the same time. Additionally, if the local laboratory results are used to make either a study drug decision or response evaluation, the results must be entered into the eCRF.

Protocol-specific requirements for inclusion or exclusion of patients are detailed in [Section 5](#). Additional tests may be performed at any time during the study as determined necessary by the Investigator or required by local regulations.

Table 2 **Protocol-Required Clinical Laboratory Assessments**

Laboratory Assessments	Parameters	
Hematology	Hematocrit Hemoglobin Hemoglobin A1c ¹ Platelet Count RBC Count RBC Indices: 
• MCV• MCH• MCHC• % Reticulocytes	WBC count with Differential: 
• Neutrophils• Lymphocytes• Monocytes• Eosinophils• Basophils
Clinical Chemistry ²	Bicarbonate BUN Calcium Chloride CPK Creatinine eGFR ³ Glucose Phosphorus Potassium Sodium	Liver Function Tests: 
• ALT• Albumin• AST• ALP• GGT• Total and Direct Bilirubin⁴

Laboratory Assessments	Parameters
	Total Protein
Coagulation ⁵	aPTT ¹ PT/INR
Fasting Lipid Profile	HDL LDL Total Cholesterol Triglycerides VLDL
Urinalysis	
 Specific gravity pH, glucose, protein, albumin, creatinine, blood, ketones, bilirubin, urobilinogen, nitrite, leukocyte esterase by dipstick, UPCR, and UACR Microscopic examination (if blood or protein is abnormal)
Pregnancy	Highly sensitive serum β -hCG (WOCBP only)
Other Tests	
 FSH (to confirm post-menopausal status)¹ Blood alcohol test¹ Urine drug screen including amphetamines, barbiturates, cocaine, opiates, cannabinoids and benzodiazepines Serology¹: HIV antibody, HBsAg, and HCV antibody⁶ COVID-19: SARS-CoV-2 test for active infection (e.g., molecular test such as PCR or viral antigen serology), and SARS-CoV-2 Ab test (IgG and IgM)
NOTES:	
¹ Only collected at Screening.	
² Details of liver chemistry increased monitoring criteria are given in Appendix 3 .	
³ eGFR to be calculated by central lab; refer to Appendix 5 for the formula.	

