- Signs, symptoms, or the clinical sequelae of a suspected drug-drug interaction.
- Signs, symptoms, or the clinical sequelae of a suspected overdose of either study drug or a concomitant medication. Overdose per se will not be reported as an AE/SAE unless it is an intentional overdose taken with possible suicidal/self-harming intent. Such overdoses should be reported regardless of sequelae.

Events NOT Meeting the AE Definition

- Abnormal laboratory findings or other abnormal safety assessments that are associated with an underlying disease present at baseline without worsening, unless judged by the Investigator to be more severe than expected for the patient's condition.
- An abnormal laboratory test that is not accompanied with other signs or symptoms.
- The disease/disorder being studied or signs, or symptoms of the disease/disorder being studied, unless more severe than expected for the patient's condition.
- Medical or surgical procedure (e.g., endoscopy, appendectomy): the condition that leads to the procedure is the AE.
- Situations in which an untoward medical occurrence did not occur (social and/or convenience admission to a hospital).
- Anticipated day-to-day fluctuations of pre-existing disease(s) or condition(s) present or detected at the start of the study that do not worsen.

Definition of SAE

An SAE is an AE that meets the following criteria:

An SAE is defined as any untoward medical occurrence that, at any dose:

a. Results in death

b. Is life-threatening

The term 'life-threatening' in the definition of 'serious' refers to an event in which the patient was at risk of death at the time of the event. It does not refer to an event, which hypothetically might have caused death, if it were more severe.

c. Requires inpatient hospitalization or prolongation of existing hospitalization

- In general, hospitalization signifies that the patient has been detained (usually involving at least an overnight stay) at the hospital or emergency ward for observation and/or treatment that would not have been appropriate in the physician's office or outpatient setting. Complications that occur during hospitalization are AEs. If a complication prolongs hospitalization or fulfills any other serious criteria, the event is serious. When in doubt as to whether "hospitalization" occurred or was necessary, the AE should be considered serious.

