## **2.3. Study Endpoints**

### **2.3.1. Primary Endpoints**

Overall safety assessed by treatment emergent AEs (TEAEs) and treatment emergent clinical safety laboratory abnormalities.

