#### 4.7.2. Definition of Baselines

The baseline value for statistical analyses of quantitative laboratory parameters is defined as the mean of all available evaluations, including any unscheduled or repeat assessments, prior to the first administration of study drug, unless otherwise specified. If there is only one evaluation prior to the first administration of study drug, then the available data from this evaluation will be used as the baseline value.

For glucose and lipid parameters, only assessments taken while fasting for at least 8 hours will be included in the baseline derivation.

The baseline value for analyses of qualitative parameters (e.g., normal/abnormal) is defined as the last evaluation prior to the first administration of study drug.

The baseline value for analyses of height, weight, body mass index (BMI), waist circumference, and electrocardiogram parameters is defined as the last evaluation prior to the first administration of study drug.

The baseline value for pharmacodynamic analytes is defined as the Week 0/Day 1 predose value.

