## **10. OTHER ASSESSMENTS**

Other assessments will be provided in by-patient data listings only; no summary tables will be provided, including but not limited to the following:

- Eligibility details including unmet eligibility criteria
- Informed consent and re-consents
- Randomization schema
- Alcohol use
- Physical examination collection information
- Serology
- Pregnancy testing
- FSH test
- Urine drug screen
- Alcohol test
- Urinalysis and Urine Microscopic Examination
- Cardiology consult
- Overdose
- Comments

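### New dipstick blood and urine microscopy findings have no planned count by arm, although laboratory abnormalities are part of the primary safety endpoint

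*SAP*

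**What the plan says.** SAP 2.3.1 gives the primary endpoint as "Overall safety assessed by treatment emergent AEs (TEAEs) and treatment emergent clinical safety laboratory abnormalities".

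Protocol Appendix 1, Table 2 lists urinalysis among the required laboratory assessments. Besides specific gravity, the panel is "pH, glucose, protein, albumin, creatinine, blood, ketones, bilirubin, urobilinogen, nitrite, leukocyte esterase by dipstick, UPCR, and UACR", with microscopy when blood or protein is abnormal. The Schedule of Activities places urinalysis at Screening, Weeks 0, 6, 12 and 16, and early termination. Protocol 2.3 gives it a safety role: "Standard hematology, chemistry, urinalysis, lipid levels, and ECGs will be obtained and monitored for abnormalities".

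SAP section 10 says "Other assessments will be provided in by-patient data listings only; no summary tables will be provided", and one of the items under that rule is "Urinalysis and Urine Microscopic Examination".

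SAP 4.7.2 contains a baseline rule that would suit dipstick results: "The baseline value for analyses of qualitative parameters (e.g., normal/abnormal) is defined as the last evaluation prior to the first administration of study drug".

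Protocol Appendix 6 includes, among events that do not meet the AE definition, "An abnormal laboratory test that is not accompanied with other signs or symptoms".

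**The concern.** The primary objective is to characterize safety against placebo. For laboratory data, that requires at least a count of patients with a new abnormality in each arm. For part of the urine panel the plan rules such a count out, and it gives no reason.

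Vital signs are a useful contrast. SAP 9.4 also leaves them out of the analyses, but it explains why (they are not entered in the EDC) and names a substitute route (clinically significant abnormalities are reported as AEs). Urinalysis has neither an explanation nor a dependable substitute. SAP 9.3 names the laboratory tests it will not summarize (coagulation, HbA1c, direct and indirect bilirubin), and urinalysis is not among them. The exclusion appears only in section 10, mostly beside administrative, eligibility and compliance items.

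At stake is whether an imbalance in silent haematuria, or in microscopy findings, would be seen in the reported results. The same trial looks for a renal benefit through proteinuria measures, so urine is examined for efficacy more fully than for harm.

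**Working it through.** There is no figure to reproduce: the sample size has no power basis and safety is descriptive. The check is to follow a new, symptom-free dipstick or microscopy finding along each route by which it could reach a by-arm result.

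- **SAP 9.3, laboratory summaries.** Limited to quantitative chemistry, lipids and hematology. Urinalysis is not included.
- **SAP 9.3.1, treatment emergent abnormalities.** Built on CTCAE grades assigned to quantitative tests. Dipstick results are not excluded in so many words, but the restriction to quantitative tests, read with the section 10 rule, leaves them out.
- **SAP 9.3.3, grade shifts.** The same restriction applies, and Table 10 names no urine test.
- **SAP 8.10.6, proteinuria biomarkers.** Urine protein, UPCR, UACR and eGFR are analysed by arm as exploratory efficacy. Blood, ketones, urobilinogen, nitrite, leukocyte esterase and microscopy are not.
- **SAP 9.5, ECG.** This is the one place with a normal-to-abnormal shift output, and it too is a listing.
- **AE tables.** Appendix 6 says twice, once among events that meet the AE definition and once among those that do not, that an abnormal test without signs or symptoms is not an AE. The note to its AE definition counts an abnormal laboratory finding as a possible AE. Capture therefore depends on which passage a site follows.
- **SAP section 10.** By-patient listing only.

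Next, which items have by-arm information elsewhere:

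- Protein and albumin: yes, through SAP 8.10.6.
- Glucose and bilirubin: a serum counterpart exists. Serum glucose and total bilirubin are in the chemistry panel, summarized under SAP 9.3, and drawn post-dose at Weeks 2, 4, 6, 8, 12 and 16 plus early termination. Urinalysis is done post-dose only at Weeks 6, 12 and 16 plus early termination.
- Blood, ketones, urobilinogen, nitrite, leukocyte esterase and reflex microscopy: no planned count by arm.

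If both parts enrol fully, the arms to be compared are 20 + 20 + 20 = 60 patients on TERN-201 at three doses and 10 + 10 = 20 on placebo, pooled under SAP 4.6. If Part 2 does not enrol, they are 20 and 10.

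**The case against.** The best defence is that the SAP does what the protocol promised. Protocol 9.4.2 calls for by-arm summaries of quantitative measurements and for CTCAE grading where it applies, and SAP 9.3 to 9.3.3 deliver that. Qualitative dipstick tables were never promised, there is no hypothesis test, and listing the results is a stated choice. This stands: there is no breach of the protocol. Protocol 9.4.2 does, however, leave further safety detail to the SAP, and the endpoint wording is not confined to quantitative tests.

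Second, SAP Appendix 1 sorts listings by treatment group, so a reader could count by hand, and SAP section 1 allows unplanned analyses in the study report. That also stands. But a hand count comes with no prespecified definition of a new abnormality and no denominator, which matters most for microscopy because it is done only on some patients.

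Third, Protocol 8.1.7 has Investigators review every laboratory report and repeat and follow clinically significant abnormalities, and Appendix 6 describes Grade 1 events as possibly asymptomatic. So individual findings would be noticed, and some would be recorded as AEs. That protects individual patients, but it does not ensure a comparison between arms.

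Fourth, the SAP 4.7.2 baseline rule does not show that a urinalysis table was planned and then dropped, since the ECG output could account for it. That is right. The rule matters here only because it makes the table easy to specify.

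**Conclusion.** The point holds as a low-cost improvement. The plan has an explicit no-summary rule for a protocol-required safety test, and as a result new dipstick blood, the remaining dipstick items listed above and reflex microscopy have no planned count by arm. Blood and microscopy are the main loss.

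Three stronger readings are tempting, and the documents do not support them:

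- That no urine safety information is compared between arms. SAP 8.10.6 and the serum tests in SAP 9.3 cover protein, albumin, renal function, glucose and bilirubin, directly or through a counterpart.
- That a silent urine abnormality can never be an AE. Appendix 6 points both ways, so the supportable conclusion is only that the AE tables cannot be relied on to capture it.
- That an imbalance could never be found. Listings sorted by arm permit a count, but none is planned.

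The documents give no expected rate of dipstick abnormality, so the size of any missed imbalance cannot be stated. The conclusion assumes that dipstick and microscopy results are not among the quantitative tests of SAP 9.3.1 and 9.3.3, which is the natural reading alongside section 10.

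**What to change.** In the SAP:

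1. Remove urinalysis and urine microscopy from the section 10 list of items that receive no summary table. Keep the listings.
2. Add to section 9.3 one descriptive table by treatment group on the Safety Analysis Set, with no test. It should show baseline (the qualitative rule in 4.7.2) against worst post-baseline result, and the number and percentage of patients with a new or worsened abnormality.
3. Cover dipstick blood and the other dipstick items, using the laboratory's own reporting categories, since the documents give no scale.
4. For reflex microscopy, use all treated patients as the denominator and show how many had microscopy done, because patients with normal dipstick blood and protein are not examined.

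Separately, the Appendix 6 passages on symptom-free laboratory abnormalities should be reconciled. The table does not depend on that.

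The cost is the programming of one extra descriptive table from data already collected. The table needs no new procedure, visit or patient, and no protocol change.

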## **11. CHANGES TO PROTOCOL PLANNED ANALYSES**

Additional exploratory efficacy endpoints were added.

## 13. APPENDICES

## APPENDIX 1. OTHER GENERAL PROGRAMMING SPECIFICATIONS

1. All output will have the following two-line header at the upper left margin:

Terns, Inc.  
TERN201-1007

and the following header at the upper right margin:

DRAFT/FINAL (as appropriate)  
Page x of y

2. Each table should be identified by in a sequential numeric order, and the table designation should be centered above the title. A decimal system within the numeric numbering (i.e., x.y and x.y.z) should be used to identify tables, listings and figures with related contents. The title is centered in initial capital characters and should include the analysis set analyzed (e.g. SS). The title and table designation are single-spaced, but are separated from the table by at least a double space.

Table No.  
First Line of Title  
Second Line of Title (if needed)  
(Analysis Set Analyzed)

3. Row labels and column headings will be in title/proper case, unless otherwise specified.
4. For variables with numeric values, include “unit” in the row label or column heading when appropriate.
5. Footnotes should be ordered as follows: abbreviations, single space, general notes, single space, specific numeric footnotes, single space, reference, and with final footnote as program name and date of the program run. The notes are aligned vertically by the left vertical border of the table. All output should have at least the footnote about the program name and date of the program run.

Abbreviations:

Notes:

- [1] Footnote 1
- [2] Footnote 2
- [3] Footnote 3

Reference Listing:

PROGRAM: program file name DDMMYY YYYY HH:MM

6. All tables will include a Reference Footnote. All figures will include a Reference Table.
7. Unless specified otherwise, all data listings should be sorted by treatment group, followed by patient number with the study center, and by visit date within patient, where appropriate.
8. All fractional numeric values should be printed with a zero to the left of the decimal point (e.g., 0.12, 0.3), unless otherwise specified.
9. Missing descriptive statistics due to non-estimability in tables, as well as missing data in patient listings should be represented as either a hyphen (“-”) with a corresponding footnote

(“ - = unknown or not evaluated”), or as “N/A” with the footnote “N/A = not applicable” whichever is appropriate.

10. Dates printed as a result in the table, listing, or graph should be printed in SAS DATE9. format (“DDMONYYYY”, e.g. 01JUL2002). Missing portions of dates should be represented on patient listings as dashes (--JUL1999). Dates that are missing because they are not applicable for the patient should be listed as “N/A”, unless otherwise specified.

## APPENDIX 2. IMPUTATION RULES FOR MISSING OR PARTIAL DATES FOR ADVERSE EVENTS AND CONCOMITANT MEDICATIONS

Date	Situation	Imputation Rule
Start Date	Only month and year are known and month and year are prior to first dose date	Use the last day of the month
	Only month and year are known and month and year are the same as first dose date	Use the first study drug administration date
	Only month and year are known and month and year are after first dose date	Use the first day of the month
	Only year is known and year is before first dose date	Use Dec 31 of that year
	Only year is known and year is same as first dose date	Use the first study drug administration date
	Only year is known and year is after first dose date	Use Jan 1 of that year
	Entire date is missing	Use the first study drug administration date
	The estimated start date is after a complete or imputed AE stop date	Use the first day of the month of the AE/CM stop date
Stop/End Date	Only month and year are known and month and year are prior to last dose date	Use the last day of the month
	Only month and year are known and month and year are the same as last dose date	Use the last dose date
	Only month and year are known and month and year are after last dose date	Use the last day of the month
	Only year is known and year is before last dose date	Use Dec 31 of that year
	Only year is known and year is same as last dose date	Use the last study drug administration date
	Only year is known and year is after last dose date	Use Dec 31 of that year
	Entire date is missing	Use the last study drug administration date
	The estimated stop date is before a complete or imputed AE start date	Use the last day of the month of the AE/CM start date
AE = adverse event, Dec = December, Jan = January		

### APPENDIX 3. ABBREVIATIONS

Abbreviation or Special Term	Explanation
ADaM	Analysis Data Model
ADL	activities of daily living
AE	adverse event
ALP	alkaline phosphatase
ALT	alanine transaminase
ANCOVA	analysis of covariance
AST	aspartate transaminase
ATC	Anatomical Therapeutic Class
AUC	area under the concentration-time curve
BMI	body mass index
BLQ	below quantification limit
CAP	Controlled Attenuation Parameter
CDISC	Clinical Data Interchange Standards Consortium
CHG	change from baseline ADaM basic dataset structure defined variable
CI	confidence interval
CK-18	cytokeratin-18
COVID-19	Coronavirus disease 2019
C max	maximal concentration
CRF	case report form
CSR	clinical study report
CTCAE	Common Terminology Criteria for Adverse Events
CTMS	clinical trial management system
CYP	Cytochrome P450
CV	coefficient of variation
DBL	database lock
eGFR	estimated glomerular filtration rate
eCRF	electronic case report form
ECG	electrocardiogram
ET	early termination
FDA	Food and Drug Administration
FSH	follicle stimulating hormone
GCP	Good Clinical Practice
GGT	gamma-glutamyl transpeptidase
HA	hyaluronic acid
HDL	high-density lipoprotein
hs-CRP	high sensitivity C-reactive protein
ICF	informed consent form
ICH	International Council for Harmonisation
IG	implementation guide
IMP	investigational medicinal product

Abbreviation or Special Term	Explanation
INR	international normalized ratio
IWRS	interactive web response system
LDL	low-density lipoprotein
LFC	liver fat content
LFT	liver function test
LLN	lower limit of normal
ln	natural log
LS	least squares
MedDRA	Medical Dictionary for Regulatory Activities
MMRM	mixed model for repeated measures
MRI-PDFF	Magnetic Resonance Imaging Proton Density Fat Fraction
NAFLD	non-alcoholic fatty liver disease
NAS	non-alcoholic fatty liver disease activity score
NASH	non-alcoholic steatohepatitis
NC	not calculated
NCA	noncompartmental analysis
NCI	National Cancer Institute
PCHG	percent change from baseline ADaM basic dataset structure defined variable
PIINP	procollagen III n-terminal peptide
PD	pharmacodynamics
PK	pharmacokinetics
PRO-C3	pro-peptide of type III collagen
Q1	25 th percentile, first quartile
Q3	75 th percentile, third quartile
REML	restricted maximum likelihood
SAE	serious adverse event
SAP	statistical analysis plan
SARS-CoV-2	severe acute respiratory syndrome coronavirus 2
SD	standard deviation
SDTM	Study Data Tabulation Model
SE	least squares mean standard error
TEAE	treatment emergent adverse event
TIMP-1	tissue inhibitor of metalloproteinases-1
ULN	upper limit of normal
WHODD	World Health Organization Drug Dictionary

